3.2.2 Pharmacokinetic and Pharmacodynamic Secondary Endpoints

- Serum (and optional synovial) AMB-05X levels
- Serum (and optional synovial) AMB-05X–binding ADA levels
- Serum (and optional synovial) CSF1 levels

4 STUDY DESIGN

4.1 Overall Design

This is a Phase 2, open-label, multiple-dose, dose-escalation study with an adaptive design that will enroll up to approximately 48 subjects with TGCT for 12 weeks of open-label treatment with IV AMB-05X. There will be a screening period of up to 4 weeks, a treatment period of 12 weeks, and a post-treatment follow-up period of 12 weeks. Each subject will receive a dose of AMB-05X every 2 or 4 weeks, for a total of 6 or 3 doses over the 12-week treatment period.

A study schema is provided in [Section 1.2](#), and the Schedule of Events is provided in [Section 1.3](#).

4.1.1 Study Visit Schedule

Study visits will occur at the following times:

- At Screening (Visit 1)
- During the Treatment Period:
 - At Baseline/Day 1 (Visit 2), within 4 weeks after Screening (subjects receive their first dose of AMB-05X)
 - At Week 2 (Visit 3), Week 4 (Visit 4), Week 6 (Visit 5), Week 8 (Visit 6), and Week 10 (Visit 7)
 - At Week 12 (Visit 8) (the end of the Treatment Period and timepoint for assessment of primary and secondary endpoints; no AMB-05X is administered)
- During the Follow-up Period:
 - At Week 14 (Visit 9) and Week 24 (Visit 10)

Refer to [Appendix 5](#) for potential changes to study conduct in the context of COVID-19 (coronavirus disease 2019).

4.1.2 Adaptive Dose Cohorts and Data Monitoring Committee

The study will enroll up to approximately 48 subjects total into up to 6 serial dose cohorts, designated Cohorts A through F. Each cohort will be composed of at least 3 and at most 12 subjects. All subjects, regardless of their dose regimen, will have a study visit every 2 weeks during the treatment period.

Dosing will begin with Cohort A at the following starting dose level and regimen:

- An initial priming dose of 4 mg/kg on Day 1
- Followed by 5 maintenance doses of 2 mg/kg administered every 2 weeks (at Weeks 2, 4, 6, 8, and 10)

The dose levels and regimens for subsequent cohorts will be determined by the Sponsor based on an ongoing analysis of available data from the previous cohort(s). The following range of dose levels and regimens may be implemented in subsequent cohorts without a protocol amendment:

Range of Dose Levels		
	Initial Dose on Day 1	Maintenance Doses
Minimum	2 mg/kg	1 mg/kg
Maximum	12 mg/kg	8 mg/kg

Although the minimum and maximum specified for the initial dose are both higher than those specified for maintenance doses, the initial dose does not have to be higher than subsequent maintenance doses. While remaining within the range specified, the initial dose may be the same as the subsequent maintenance doses, or the initial dose may be a higher, priming dose.

Allowable Regimens			
	Frequency	# Doses	Schedule
Minimum	Every 4 weeks	3 doses	Initial dose on Day 1
			2 maintenance doses, at Weeks 4, 8
Maximum	Every 2 weeks	6 doses	Initial dose on Day 1
			5 maintenance doses, at Weeks 2, 4, 6, 8, 10

Thus, the lowest dose that a cohort could receive would be an initial dose of 2 mg/kg on Day 1, followed by 2 maintenance doses of 1 mg/kg every 4 weeks (at Weeks 4 and 8). The highest dose that a cohort could receive would be an initial dose of 12 mg/kg on Day 1, followed by 5 maintenance doses of 8 mg/kg every 2 weeks (at Weeks 2, 4, 6, 8, and 10).

A Sponsor DMC composed of qualified medical/clinical representatives from the Sponsor will review the available safety, tolerability, PK, PD, and efficacy data on an ongoing basis and provide recommendations regarding appropriate next steps in study conduct. Study enrollment will begin with an initial 3 subjects in Cohort A. The DMC will begin to review study data after the first 3 subjects complete Week 6 and will continue to review data throughout the study (each time 3 additional subjects [from any cohort] complete Week 12). Whenever a new dose is instituted during the study, the DMC will again review the available data once 3 subjects have completed Week 6 at the new dose.

The DMC will pay special attention to any clinically significant AEs. Clinically significant AEs include DLTs, AEs leading to discontinuation, and AESIs, all considered at least possibly related to study drug. A DLT is defined as any Grade 3 or higher AE or SAE considered at least possibly related to study drug. AESIs are defined in [Section 7.3.8.2](#).

Based on the recommendations of the DMC, the Sponsor may implement any of the following decisions without a protocol amendment, in the manner of a 3+3 dose escalation study design:

- If none of the first 3 subjects of a cohort experiences a clinically significant AE after 12 weeks on study drug, the Sponsor may elect to begin enrollment of the next cohort.

- If exactly 1 subject among the first 3 subjects of a cohort experiences a clinically significant AE, an additional 3 subjects will be enrolled into that cohort. If only 1 of the 6 subjects experiences a clinically significant AE, the Sponsor may then elect to proceed with enrollment of the next cohort.
- If exactly 2 subjects among the first 3 subjects of a cohort experience a clinically significant AE, the Sponsor will suspend enrollment in that cohort, and the DMC will make recommendations on next steps, such as suspending further enrollment in that cohort, enrolling another 3 subjects into the cohort, or initiating another cohort at a lower dose.
- If exactly 2 subjects in a 6-subject cohort experience a clinically significant AE, the Sponsor may elect to enroll an additional 3 subjects into that cohort at the same dose. If no additional clinically significant AEs occur, the Sponsor may then elect to proceed with enrollment of the next cohort.
- If ≥ 3 subjects in a 3- or 6-subject cohort experience a clinically significant AE, the Sponsor will suspend dosing and enrollment in that cohort and/or any further dose escalation in the study. Additional subjects may be enrolled at a lower dose.
- If data from the first 3 subjects in a cohort to complete treatment indicate suboptimal drug exposure and efficacy, and there are no significant safety issues such as clinically significant AEs, the Sponsor may elect to discontinue further enrollment in that cohort and proceed directly to the next cohort.
- If safety permits according to the rules above (ie, if $\leq 1/3$ of the previous subjects in the cohort experience a clinically significant AE), the Sponsor may elect to enroll up to 12 subjects per cohort for more conclusive data.
- Following the rules above, the Sponsor may elect to enroll the subsequent cohort in a staggered / overlapping manner (initiating enrollment in the next cohort while the current cohort is still completing the study or still enrolling) or sequentially (waiting until more complete data are available from the current cohort before initiating the next cohort).
- The Sponsor may discontinue further enrollment and/or suspend/terminate the study (see [Section 10.1.7](#)).

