6.3 Measures to Minimize Bias: Randomization and Blinding

If there is concurrent enrollment of multiple cohorts, subjects will be randomized to a cohort via the interactive web response system (IWRS). There is no blinding except for the blinding of the central radiologist to a subject's dose.

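### After 3 or more clinically significant AEs in a 3- or 6-subject cohort, suspending dose escalation alone satisfies the rule, and no DMC review is required before the next dose

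*Combined protocol and SAP*

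**What the plan says.** Section 4.1.2 and the synopsis (Section 1.1) carry the same bullet. With 3 or more affected subjects in a 3- or 6-subject cohort, "the Sponsor will suspend dosing and enrollment in that cohort and/or any further dose escalation in the study". Enrollment at a lower dose may follow.

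The bullets share a lead-in under which, on the DMC's recommendations, "the Sponsor may implement any of the following decisions without a protocol amendment". For exactly 2 of the first 3 subjects the bullet is firmer: "the Sponsor will suspend enrollment in that cohort, and the DMC will make recommendations on next steps".

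The fixed DMC reviews in Section 4.1.2 follow visit completion. One falls after the first 3 subjects complete Week 6, then "each time 3 additional subjects [from any cohort] complete Week 12", and, for a new dose, "once 3 subjects have completed Week 6 at the new dose". The DMC also has a general duty of continuing review. Section 7.3.8 asks it to weigh clinically significant AEs when advising whether dosing or enrollment goes on.

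Cohorts may overlap, which includes "initiating enrollment in the next cohort while the current cohort is still completing the study or still enrolling". Section 6.3 plans for this too: "If there is concurrent enrollment of multiple cohorts, subjects will be randomized to a cohort".

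**The concern.** This is the only escalation bullet that names a suspension of dosing, and the and/or makes that suspension optional. The worse outcome (3 or more) therefore has a looser required action than the milder one (2 of 3), for which an enrollment stop and DMC recommendations are both stated. Nothing ties a DMC review to the moment the third event is known. With dosing every 2 weeks, subjects in the affected cohort could receive further drug before anyone is obliged to decide whether they should.

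A secondary question is what happens to a higher-dose cohort that is already open when the lower cohort reaches the count. The bullet does not say.

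**Working it through.** The documents state no operating characteristic for this rule, so there is no figure to reproduce. The check is a reading of the text plus supporting arithmetic.

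**1. What complies.** Let A be suspension of dosing and enrollment in the cohort, and B suspension of further escalation. A alone, B alone, or both satisfy the bullet. Under B alone, no dosing hold is required.

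| Outcome | Enrollment stop | DMC recommendation named in the bullet | Dosing hold |
|---|---|---|---|
| Exactly 2 of first 3 | Required | Yes | Not named |
| 3 or more of 3 or 6 | Only under A | No (lead-in only) | Only under A |

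**2. What the neighboring bullets already block.** Moving up needs 0 of 3, 1 of 6, or 2 of 6 followed by no event in 3 more. Expansion to 12 needs at most 1/3 affected; 3/3 is 100% and 3/6 is 50%. So no rule supports more same-dose enrollment or a new higher-dose cohort.

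**3. How often the rule is reached.** Count only automatic steps: 3 of 3, or 1 of 3 and then at least 2 of the 3 subjects who must be added. With a common, independent per-subject probability p,

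P = p³ + 3p(1−p)² × [3p²(1−p) + p³].

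Inputs: p = 0.20 is an assumption. The others come from Section 2.4.1: 0.28 = 7/25 (related Grade 3 or higher AEs) and 0.44 = 11/25 (related periorbital edema, an AESI at any grade).

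| p | 3 of 3 | via added three | P | share via added three |
|---|---|---|---|---|
| 0.20 | 0.0080 | 0.0399 | 4.8% | 83% |
| 0.28 | 0.0220 | 0.0833 | 10.5% | 79% |
| 0.44 | 0.0852 | 0.1699 | 25.5% | 67% |

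The exact 95% interval for 7/25 is 12% to 49%, giving P from 1.3% to 30.7%. For 11/25 it is 24% to 65%, giving 7.7% to 44.7%. If three more subjects were also enrolled after every 2-of-3 result, add 3p²(1−p) × [1−(1−p)³]; the totals become 9.5%, 21.1% and 52.3%.

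**4. Drug given before a fixed review.** Cohort A totals 4 + 5×2 = 14 mg/kg. The highest regimen totals 12 + 5×8 = 52 mg/kg.

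| Doses | Cohort A | Highest regimen |
|---|---|---|
| Weeks 2, 4, 6 (up to the Week 6 visit) | 6/14 = 43% | 24/52 = 46% |
| Weeks 8, 10 (Week 6 to Week 12) | 4/14 = 29% | 16/52 = 31% |
| Weeks 2 to 10 (all after Day 1) | 10/14 = 71% | 40/52 = 77% |

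The third row concerns the three added subjects. Their dose is no longer new, so the Week 6 trigger does not cover them, and the review tied to their own progress comes at Week 12. All rows are upper bounds, because the documents give no event timing and reviews triggered by other subjects may fall sooner. If the added three start near the first three's Week 6, and the first three's Week 12 counts as a trigger, that review falls near the added three's Week 6. If they start after the first three's Week 12 and no other cohort is running, nothing earlier is fixed.

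**5. Higher-dose cohort already open.** Within a 3- or 6-subject cohort this needs 0 of 3, then 3 of 3 on expansion: [p(1−p)]³ = 0.4% (p = 0.20), 0.8% (0.28), 1.5% (0.44), with a maximum of 1.6% at p = 0.50. It also needs two Sponsor elections: opening the next cohort at a higher dose and expanding the current one. The formula assumes that subjects counted as event-free stay so.

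**The case against.** The best reply is that dosing decisions are already assigned. Section 7.3.8 makes continuing or suspending dosing a DMC topic, and Section 4.1.2 requires continuing review. AESIs go on a dedicated form (Section 7.3.8.2), SAEs are reported within 24 hours (Section 7.3.6), and Investigators may stop drug (Section 4.4) or reduce the dose after a DLT (Section 4.1.3). This stands as far as it goes: an early review is possible, and likely in practice. But none of these provisions requires a review or pause when the count is reached, and the Investigator measures work subject by subject.

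The second reply is proportionality. The trigger includes any-grade liver-enzyme rises and periorbital edema. Section 2.4.1 describes the edema as mostly resolving and managed without intervention, and reports no related serious or fatal AEs and one related discontinuation. This also stands, and it argues against an automatic dosing hold for every firing. It does not argue against a prompt review, and related Grade 3 or higher AEs, which would be DLTs here, occurred in 28% of that study's subjects.

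A reader might infer that the permissive lead-in turns the obligation into an option. The full sentence places the decisions after DMC recommendations and says that they need no amendment; it need not weaken the bullet's own verb. A reader might also infer that the Sponsor could go on enrolling at the same dose or open a new higher-dose cohort. Step 2 shows that the neighboring rules give no basis for either.

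**Conclusion.** The point holds in a limited form. In a 3- or 6-subject cohort, suspending escalation alone meets the rule, and no DMC review is required before subjects in that cohort are dosed again. The already open higher-dose cohort is a rare secondary case, at most 1.6% before two Sponsor elections.

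The 4.8% to 25.5% is the chance that a cohort reaches the rule. It should not be read as the chance that dosing wrongly continues or that harm occurs; the documents support no such figure. The rates of 28% and 44% are single components of a composite trigger, from advanced-cancer patients at doses up to 20 mg/kg, so transfer to TGCT is uncertain in either direction. The calculation also assumes equal, independent risks. The 71% is everything scheduled after Day 1 for an added subject, not expected exposure after a third event. The dose figures assume that the three subjects start together.

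**What to change.** Reword the bullet in Sections 1.1 and 4.1.2 to this effect: once 3 or more subjects in a 3- or 6-subject cohort have a clinically significant AE, enrollment in the affected cohort and all further escalation stop, including new enrollment in any open higher-dose cohort. The DMC meets ad hoc, where possible before the next scheduled dose, to decide whether dosing in the affected cohort, and in any open higher-dose cohort, continues, is reduced or stops. If any of the events is a DLT, dosing in the affected cohort is held until that meeting.

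Keep the sentence allowing enrollment at a lower dose. Define higher as a higher initial dose, a higher maintenance dose or a higher planned cumulative mg/kg. Cumulative dose alone is not enough: 12 + 1 + 1 = 14 mg/kg equals Cohort A's total with three times its initial dose.

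This is a cheap improvement: one bullet in two places and one definition, by amendment under Section 10.1.6. The price is some Sponsor discretion, an extra internal DMC review and an occasional delayed or missed dose. Visit windows during dosing are 2 to 3 days either side, so a slow review could cost one dose: 2/14 = 14% of planned mg/kg in Cohort A, or 1 of 3 doses on a 4-weekly regimen. Limiting the automatic hold to DLTs keeps this small when the events are mild.

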4.1.3 Subject Dose Reduction

Enrolled subjects will begin treatment at the planned dose levels for their assigned cohorts. The Investigator may exercise his/her clinical judgment and consider a reduction in an individual subject's maintenance dose (eg, from 2 mg/kg to 1 mg/kg, 4 mg/kg to 2 mg/kg, or 8 mg/kg to 4 mg/kg) for subjects who experience a DLT. Before implementing a dose reduction for a subject, the Investigator should contact the Medical Monitor to discuss the case. Subjects who are unable to tolerate the lowest dose level specified in [Section 4.1.2](#) will have study drug discontinued.

[figure not shown]
4.2 Justification for Dose

The proposed starting dose level for Cohort A is an initial priming dose of 4 mg/kg IV, followed by 5 maintenance doses of 2 mg/kg IV every 2 weeks thereafter, for a total of 6 doses over 12 weeks. This dose level is well supported by a 14-week Good Laboratory Practice (GLP)

toxicology study with QD IV dosing in cynomolgus monkeys (see [Section 2.3](#)) and by the first-in-human and pembrolizumab-combination clinical studies of IV AMB-05X (see [Section 2.4](#)).

[Figure 1](#) shows simulated AMB-05X concentrations in serum and synovial fluid for the Cohort A starting dose level. The projected serum drug levels are modeled from published Phase 1 data ([Papadopoulos, 2017](#)). The extrapolated synovial fluid partitioning is based on published results with other antibodies ([Stepensky, 2012](#) and AmMax internal data). The Cohort A starting dose level should yield serum and tissue AMB-05X concentrations previously shown to be safe and achieve steady-state drug levels by the end of the treatment period. The projected synovial AMB-05X concentrations achieve a target estimated level for efficacy (indicated by the y-axis arrow).

Figure 1. Simulated Serum and Synovial Fluid AMB-05X Concentrations for the Cohort A Starting Dose Level

4.3 End of Study Definition

A subject is considered to have completed study treatment if the subject has completed all 12 weeks of the Treatment Period.

A subject is considered to have completed the study if the subject has completed all study visits, including visits during the Follow-up Period.

The end of the study is defined as the date of the last study visit of the last subject in the study.

4.4 Subject Early Termination

Subjects may choose to discontinue study drug or withdraw from study participation at any time, for any reason, specified or unspecified, without prejudice. The Investigator and/or Sponsor may also discontinue a subject's study drug or withdraw the subject from the study at any time. The

Investigator will discontinue a subject's study drug if the Investigator concludes that continuation would be detrimental to the subject's safety or well-being.

Reasons for premature discontinuation of study drug / withdrawal from the study may include:

- Pregnancy
- Adverse event
- Death
- Physician decision
- Subject decision
- Lack of efficacy
- Protocol violation
- Study termination by the Sponsor
- Lost to follow-up
- Other, to be specified

If ET occurs for any reason, the Investigator must make every effort to determine the primary reason for the ET and record this information on the eCRF. The Investigator will also schedule ET procedures for a subject who terminates early but does not withdraw consent for study participation (see [Section 8.11](#)). ET procedures consist of Visit 8 (Week 12), Visit 9 (Week 14), and Visit 10 (Week 24) (whichever visits the subject has yet to complete at the time of ET). Subjects who discontinue study drug as the result of an AE will also be followed according to [Section 7.3.4](#). Subjects who withdraw consent will be considered withdrawn from further study participation.

If a subject fails to appear for study visits without stating an intention to withdraw, the site must make every effort to regain contact with the subject, including making 3 telephone calls to the subject and, if necessary, sending a registered letter to the subject's last known mailing address. Attempts to contact the subject will be documented in the subject's site file. If the subject continues to be unreachable, the subject will be considered lost to follow-up and thus withdrawn from the study.

5 STUDY POPULATION

This study will enroll up to approximately 48 adult subjects with local or diffuse TGCT in the United States and Europe.

5.1 Inclusion Criteria

A subject may be included in this study if ALL of the following criteria are met.

1. Male or female ≥ 18 years of age.
2. Able to communicate well with study staff and understand and comply with the requirements of the study. Reads and voluntarily signs the ICF and the HIPAA authorization (if applicable) before the conduct of any study-specific procedures.
3. TGCT that has been histologically confirmed by a pathologist. If the diagnosis has not been previously histologically confirmed, biopsy with histological confirmation is required before enrollment.
4. Measurable disease as defined by RECIST v1.1 (except with a minimum size of 2 cm), assessed from MRI scans by a central radiologist.
5. If subject uses prescription analgesic, subject must be on a stable prescription analgesic regimen during the 2 weeks before Baseline.
6. Agrees to follow contraception guidelines (see [Section 5.3](#)).
7. Adequate hematologic, hepatic, and renal function at Screening, defined by:
 - Absolute neutrophil count $\geq 1.5 \times 10^9/L$
 - AST and ALT $\leq 1.5 \times ULN$
 - Hemoglobin $> 10 \text{ g/dL}$
 - Total bilirubin $\leq 1.5 \times ULN$ (elevated bilirubin secondary to a known, relatively benign condition [eg, Gilbert's syndrome] is not exclusionary)
 - Platelet count $\geq 100 \times 10^9/L$
 - Serum creatinine $\leq 1.5 \times ULN$
8. Willing and able to complete the PROMIS Physical Function Scale, Worst Stiffness NRS, BPI, and EQ-5D-5L throughout the study.

5.2 Exclusion Criteria

A subject will be excluded if ANY of the following criteria is met.

1. Use of any investigational drug within 4 weeks or 5 half-lives (whichever is longer) before Baseline.
2. Use of pexidartinib, any other oral tyrosine kinase inhibitor (eg, imatinib or nilotinib), or any biologic treatment targeting CSF1 or CSF1R within 3 months before Baseline.

3. Current or prior radiotherapy within 3 months before Baseline
4. Current or prior active cancer within 3 years before Baseline that requires/required therapy (eg, surgery, chemotherapy, or radiation therapy), except adequately treated basal or squamous cell carcinoma of the skin, melanoma in situ, carcinoma in situ of the cervix or breast, or prostate carcinoma not requiring treatment apart from active surveillance.
5. Known metastatic TGCT or malignant transformation of diffuse-type TGCT.
6. Any history of complex or reconstructive surgery on the affected joint (eg, involving plates, screws, or metal implants).
7. HCV or HBV or known active or chronic infection with HIV.
8. Known active TB.
9. Significant concomitant arthropathy in the affected joint, serious illness, uncontrolled infection, or a medical or psychiatric history that, in the Investigator's opinion, would likely interfere with the subject's study participation or the interpretation of the subject's results.
10. A woman who is pregnant or breastfeeding. For women of childbearing potential, a positive pregnancy test at either Screening or Baseline will be exclusionary.
11. A screening QTcF ≥ 450 ms (men) or ≥ 470 ms (women)
12. MRI contraindications (eg, pacemaker, loose metallic implants)
13. History of hypersensitivity to any ingredient in the study drug.
14. History of drug or alcohol abuse within 3 months before Baseline.
15. Has any other severe acute or chronic medical or psychiatric condition or clinically significant laboratory abnormality that may increase the risk associated with study participation/treatment, interfere with interpretation of study results, or, in the Investigator's opinion, make the subject inappropriate for this study.
16. A person who is held in detention as the result of a judicial or official decision or who is in a subordinate relationship to the Sponsor or Investigator.
17. A subject who, in the opinion of the Investigator, should not participate in this study for any reason, including instances where the subject's stability or ability to comply with study requirements is in question.

